1.0 Objectives

1.1 Describe the purpose, specific aims, and/or objectives.

The goal of this research is to determine if the Tangible Boost system adequately replenishes the HydraPEG coating on the surface of a rigid contact lens. HydraPEG is a soft and rigid contact lens coating, primarily composed of polyethylene glycol, which is covalently bound to the surface of a contact lens. The HydraPEG coating is intended to improve wettability and comfort with rigid lenses, and is currently FDA approved. HydraPEG can be applied to soft or rigid contact lenses, but the coating naturally diminishes from the surface of the lens over time (due to cleaning, and blinking over the surface of the contact lens). Tangible Science, the company that produces HydraPEG, has recently come out with a new product called Tangible Boost, intended to be used every 30 days and replenish the coating on the surface of the lens.

Tangible Boost (also known as HydraPEG Replenish in some of the FDA documents) is a solution composed on the same components of the HydraPEG coating). Essentially, Tangible Boost solution is the HydraPEG coating, it is just in solution that can be used at home by the subjects after the initial HydraPEG is applied at the lens manufacturing lab. The Tangible Boost kit consists of two unit dose HydraPEG solutions (components A and B), as well as a barrel case, and the lens wearers are instructed to empty the two vials into the case and soak their lenses for 30 minutes every 30 days to replenish the coating. This product configuration has been optimized to facilitate ease of use for the patient.

This is a study to evaluate the efficacy of Tangible boost to replenish the HydraPEG coating on rigid gas permeable (scleral and corneal) contact lenses.

1.2 State the hypotheses to be tested.

We hypothesize that the Tangible Boost replenishing system will re-build the HydraPEG coating that naturally diminished from the contact lens surface over time, and improve the comfort and visual performance of HydraPEG coated rigid gas permeable lenses. We anticipate that this be shown by improved patient symptoms and lens wettability after treatment with Tangible Boost.

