10.0 Procedures Involved

10.1 Describe and explain the study design.

Once a subject has been identified, the initial visit will be scheduled. During the experimental day, informed consent will be completed, and the subjects will complete the following tasks: (1) an investigator will conduct visual acuity assessments of both eyes (Snellen). (2) The subjects will be asked to complete a survey (on contact lens satisfaction). (3) After the survey, the subject will sit with their lenses for assessment using the Keratograph topographer. (4) After topography, slit lamp assessment of the rigid lenses, and then of the cornea and conjunctiva (after lens removal) with and without Lissamine Green staining will be done.

At visit one, the following additional task will be performed: (1) The subject will be asked to sit for a corneal or scleral lens fitting visit (based on what they wear habitually), where the investigator will fit the subject with a commercially available scleral or corneal lens. All subjects will be refit into the Advanced Vision Technologies (AVT) brand of rigid lenses, manufactured at AVT Technologies in Colorado. If they already wear the AVT brand, the lens parameters will simply be re-ordered. All lenses will undergo a diagnostic fit with an AVT lens. The parameters available at AVT are similar to those available at all other major labs in the US.

A second visit will be to evaluate the fit of the ordered study lenses (which will have been coated with the HydraPEG coating), and will be for the dispense of the lenses. In addition to evaluating the lenses, the subjects will be asked to complete a short survey on their satisfaction with their current lenses. After this visit, the subjects will then wear the lenses for 30 days, on a daily basis as they habitually would, cleaning the lenses with ClearCare hydrogen peroxide cleaning system, a commonly used commercially available soft and rigid contact lens cleaner. After 30 days of lens wear, they will report for visit 3.

At the third visit, the same testing will be performed from visits 1 and 2, the subject will also be given an additional survey regarding the satisfaction with the HydraPEG lenses, and then the Tangible Boost kit or the placebo kit (consisting of

Page 9 of 22 Revised: July 24, 2017

two vials with Unique pH) solutions will be dispensed (randomized) to store their lenses in for 30 minutes that night.

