The solution will be dispensed and the subjects trained on its use, and the subjects will be asked to store their lenses in the given solution for 30 minutes that evening, and then transfer their lenses to Unique pH multipurpose rigid lens solution for overnight storage. For the initial training with the Boost or placebo system, the users will undergo an approximately 60-minute user training in which there will be visual and audio recording and still photographs taken in order for a human factors company (Userwise) to analyze the usability of the product. The investigator at the study visit will act as the monitor for the training session. This recorded training step was specifically designed to allow for proper evaluation of the usability of the product, which they will report to the FDA to ensure usability. At the initial visit, the subject will have indicated on the informed consent form whether they agree to participate in the recorded portion of the training. If they do not participate in the recording, they can still be trained and participate in the study.

The subjects will report to the Ocular Surface Institute the next day for Visit 4, at which time the comfort and visit tests will occur again, and an additional survey to evaluate the boost treatment will be given. After visit 4, the subjects will continue to wear the study lenses daily for an additional 60 days, treating their lenses again in the Boost or placebo solution at the midpoint between visit 4 and 5 (30 days after the first treatment with Boost), otherwise cleaning nightly with ClearCare, and will then report to the clinic again 30 days after the midway treatment (approximately 90 days after the initial HydraPEG dispense). The same visit testing will be done at this final and 5th visit, and a final short survey will be done, and then the lenses will be collected from the subjects and sent back to Tangible Science, Inc. for their internal testing of the lenses (no involvement of the UH research team). At this time the study will conclude.

The following table outlines each of the study visits and tells what procedures will be done at each visit:

Procedure	Length of Time Required for	Frequency of Repetition
VISIT 1: Initial Evaluation		
Informed consent & HIPAA	35 minutes	Once
General History and medications	5 minutes	Once per visit
Visual Acuity	5 minutes	Once per visit

Page 10 of 22 Revised: July 24, 2017

Questionnaires (CLDEQ8 + VAS)	10 minutes	Once per visit

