Statistical Analysis: Each individual will act as their own control to measure differences in pre and post contact lens measurements (paired non-parametric statistics), and this baseline data will be compared to normative data available for a soft contact lens wearing population. Descriptive statistics will also be employed to evaluate the overall response of the eye to a rigid lens with and without HydraPEG and with and without Tangible Boost.

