Evaluation of Tangible Boost Replenishing System

	OD		OS
		_	e
		_ Comments	
erform Ker	atograph NIBUT		
OD:	NIKf-BUT "until k	olink" (first break up)	
	NIKavg-BUT "unt	til blink" (average break up)	
	Level:		
	NIKf-BUT "25 sec	conds" (first break up)	
	NIKavg-BUT "25	seconds" (average break up)	
	Level:		
OS:	NIKf-BUT "until k	olink" (first break up)	
	NIKavg-BUT "unt	til blink" (average break up)	
	Level:		
	NIKF-BLIT "25 see	conds" (first break up)	
	Level:		
			
ilit lamn eva	am (after lens remo	oval)	
iit iaiiip exe	OD	ovaij	OS
		Lids and lashes	
		Conjunctiva	
		Sclera	
		Cornea	
		Cornea 	
			

2

[figure not shown]

Subject: _____

[figure not shown]
Date: _____/_____

Evaluation of Tangible Boost Replenishing System

13. Corneal Fluorescein Staining (0-4 grading)

TOTAL Score: OD _____ OS ____

14. Gift card given? \square_1 Yes \square_2 No

Subject	•				
Dato:	1	1			

OPTIONAL VISIT FOR LENS RE-FITTING (TO BE USED IF THERE ARE FOLLOW-UP VISITS NEEDED FOR PROPER LENS FIT)

L .	Time of Day (military time) ::		
2.	Hours of Rigid lens wear today:		
3.	Current Cleaning solution:		
.	Currently wearing study lenses? \Box_1 Yes (if yes, evaluate lenses and \Box_2 No (if no, apply study lenses)	then remove and apply new ler	nses)
5.	Slit Lamp Evaluation of Study Lens test lenses if dispenses test lenses applied the habitual lenses	sed at last visit	ng evaluated)
	OD	Movement Centration Apical Clearance Limbal Clearance Scleral Landing Zone Comments	OS
.		of Study Lenses (only to be used test lenses applied today	d if test lenses for dispense were not
	OD	Movement Centration Apical Clearance Limbal Clearance Scleral Landing Zone Comments	OS
			Examiner Initials:

Page 1 of 6

Subject: _		
Date:	_/	/

DD:	OS:
Perform Ker	atograph NIBUT (to be performed only if lenses will be dispensed today)
OD:	NIKf-BUT "until blink" (first break up)
	NIKavg-BUT "until blink" (average break up) Level:
	NIKf-BUT "25 seconds" (first break up)
	NIKavg-BUT "25 seconds" (average break up) Level:
OS:	NIKf-BUT "until blink" (first break up) NIKavg-BUT "until blink" (average break up) Level:
	NIKf-BUT "25 seconds" (first break up) NIKavg-BUT "25 seconds" (average break up) Level:
Indicate CL (lesign parameter changes needed

CONTACT LENS QUESTIONNAIRE-8 (CLDEQ-8)

1. Questions about **EYE DISCOMFORT**:

- a. During a typical day in the past week, **how often** did your eyes feel discomfort while wearing your contact lenses?
 - 0 Never
 - 1 Rarely
 - 2 Sometimes

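### Boost and placebo are randomised, but the plan commits to no between-arm test; the only test Section 10.2 names is a within-subject pre/post comparison that cannot isolate Boost

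*Combined protocol and SAP*

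**What the plan says.** Section 1.2 words the hypothesis as improvement after Boost and does not mention placebo: "We anticipate that this be shown by improved patient symptoms and lens wettability after treatment with Tangible Boost". Section 10.1 nevertheless sets up a controlled comparison. At Visit 3 the Boost or placebo "solutions will be dispensed (randomized"), and the assigned product is used again midway between Visits 4 and 5.

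The analysis is described in two places.

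- **Section 10.2:** "Each individual will act as their own control to measure differences in pre and post contact lens measurements (paired non-parametric statistics"). Baseline is also compared with soft-lens norms. Response with and without HydraPEG, and with and without Boost, is to be described rather than tested.
- **Section 25.1:** data are analysed for change from baseline to test. An open list of methods follows: t-tests, signed-rank tests, analysis of variance, general linear models, correlation and regression.

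Neither place names treatment arm as a factor, a visit or an endpoint, and neither defines *pre* and *post*. Section 9.1 lists four primary endpoints without a visit or contrast. Section 5.2 takes the first 30 eligible completers, and Section 16.3 drops data from anyone who withdraws.

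**The concern.** The study's stated goal is to find out whether Boost replenishes the coating, and the placebo arm is the design feature that can answer this. The plan does not commit to using it for a test. Any within-arm change includes whatever the placebo arm also goes through over the same interval. A paired test can therefore credit Boost with a change common to both arms. It can also show nothing when Boost has prevented a decline that only the placebo arm would reveal. Because arm term, visit and endpoint are all open, the between-arm analysis could also be chosen after the data are seen.

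**Working it through.** **1. The plan's own number.** Section 5.2 expects about 20% screen failure or dropout and 30 completers: 30/(1 − 0.20) = 37.5, so 38, which lies inside the stated 35-40. The 30 itself has no effect size, SD, significance level or power behind it, so it cannot be reproduced.

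**2. What each pre/post reading measures.** From Section 10.1, taking dispensing (Visit 2) as day 0:

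| Event | Approximate day |
|---|---|
| Visit 3; first soak that evening | 30 |
| Visit 4 | 31 |
| Second soak | 60 |
| Visit 5 | 90 |

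- *Visit 1 as pre.* "All subjects will be refit into the Advanced Vision Technologies (AVT) brand of rigid lenses", and the lenses arrive with the initial HydraPEG coating. Both arms receive both, so the change mixes them with Boost.
- *Visit 3 to Visit 4.* "The subjects will report to the Ocular Surface Institute the next day for Visit 4". The change includes placebo response and repeat testing. The CLDEQ-8 asks about "During a typical day in the past week", so about 6 of its 7 recall days precede the first soak.
- *Visit 3 to Visit 5.* "After 30 days of lens wear, they will report for visit 3", counted from a fresh coating. For Visit 5 subjects "will then report to the clinic again 30 days after the midway treatment". Both visits therefore fall about 30 days after a coating or treatment. If Boost fully restores the coating and it then wears off at the same rate, the expected change in the Boost arm is roughly zero. The benefit would appear only as a decline in the placebo arm.

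**3. Illustrative size.** The documents give no effect size, SD or allocation ratio. Assumed: 15 per arm, normal changes with SD 1, two-sided 5%, 10,000 simulated trials per row.

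(i) No Boost effect, same shift in both arms, proportion of trials significant:

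| Common shift | Signed-rank, Boost arm | Signed-rank, all 30 | Boost arm significant, placebo arm not | Rank-sum between arms |
|---|---|---|---|---|
| 0.3 SD | 18% | 34% | 15% | 4-5% |
| 0.5 SD | 42% | 74% | 24% | 4% |
| 0.8 SD | 80% | 99% | 16% | 4-5% |

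The all-30 column is shown because the plan does not say whether the paired test is run by arm or on everyone.

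(ii) Boost arm unchanged, placebo arm declines:

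| Placebo decline | Signed-rank, Boost arm | Rank-sum between arms | t-test between arms (exact) |
|---|---|---|---|
| 0.5 SD | 5% | 23% | 26% |
| 0.8 SD | 5% | 53% | 56% |
| 1.0 SD | 5% | 72% | 75% |

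The exact t power uses 28 df and noncentrality d/√(1/15 + 1/15) = d/0.365.

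**4. Precision of the between-arm test (80% power, t).**

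- Detectable difference: 1.06 SD of change with 15/15, 1.12 SD with 20/10.
- A paired test detects 0.53 SD on 30 subjects, or 0.78 SD on 15.
- 95% CI half-width with 15/15: t(28) × √(2/15) = 2.048 × 0.365 = 0.75 SD.
- In SDs of the follow-up value, with correlation r between Visit 3 and follow-up, the change score detects 1.06√(2(1 − r)) and the adjusted analysis about 1.06√(1 − r²):

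| r (assumed) | Change score | Adjusted for Visit 3 |
|---|---|---|
| 0.3 | 1.25 | 1.01 |
| 0.5 | 1.06 | 0.92 |
| 0.7 | 0.82 | 0.76 |

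**The case against.** The strongest reply is that an unspecified test is not an excluded one. Section 25.1 allows analysis of variance, general linear models and regression, any of which could carry an arm term. The descriptive with/without-Boost comparison in 10.2 may already mean Boost against placebo. The study is a pilot meant to inform later power calculations, so a formal test matters less. The paired wording may be aimed at habitual versus study lenses, where pairing is appropriate. The simulated shifts are assumptions.

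Much of this is fair. An arm comparison is permitted, pairing does suit the lens question, and the simulation shows a general property of paired tests rather than anything measured here. The recall problem is specific to the CLDEQ-8: the comfort scale worded for the present moment and the Visit 4 survey items about that day do not share it, and the CLDEQ-8 problem would persist under a between-arm test.

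The central point stands. The descriptive phrase could equally mean before versus after Boost, and a list of methods fixes neither contrast, visit nor endpoint. Pilot status excuses low power, but it does not excuse leaving the randomised contrast unnamed. Section 5.3 speaks of reaching significance and 25.1 of hypothesis testing, so inference is intended. A later Boost-versus-placebo trial would also need the between-arm difference and its SD.

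**Conclusion.** The concern holds, on the text alone. Subjects are randomised to Boost or placebo, no section specifies a test between them, and the one test 10.2 names cannot attribute a change to Boost under any of the three readings examined.

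The numbers are illustrative and rest on 15 per arm, normal changes and the assumed shifts. On those terms, a common shift of 0.3-0.8 SD would produce a significant Boost-arm result in about 18-80% of trials with no Boost effect. From Visit 3 to Visit 5, a Boost that fully offsets a placebo-arm decline would be flagged by its own paired test only about 5% of the time. This should be corrected before any outcome data are analysed.

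**What to change.** Amend Sections 10.2 and 25.1 as follows.

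- State that the Boost question is answered by the randomised Boost-versus-placebo comparison of change from Visit 3, or of the follow-up value adjusted for the Visit 3 value. Report the estimate with a 95% CI as pilot evidence.
- Name one lead endpoint and one visit that fit each other. CLDEQ-8 at Visit 4 mostly covers days before Boost.
- Use a rank-based or ordinal method for graded staining, and one value per subject for measures taken on each eye.
- Keep paired tests for habitual versus coated lenses. Treat within-arm changes around Boost as descriptive.
- Because only completers are analysed, label the result a completer comparison and give the numbers randomised and completing by arm.
- State in 5.3 that the comparison rests on about 15 per arm if allocation is 1:1.

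Separately, Section 10.1 describes routine cleaning with ClearCare while the appended handling instructions specify Unique pH. These must be reconciled.

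**Cost.** No new subjects, visits or data. Choosing the lead endpoint from the four primaries is a real decision for the investigators. The price is low precision: 80% power only for about 1.06 SD and a CI of about ±0.75 SD. The paired test on 30 looks sharper at 0.53 SD, but it answers a different question. Adjusting for Visit 3 recovers some precision, for example 0.92 against 1.06 SD at an assumed correlation of 0.5.

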2.0 Background

2.1 Describe the relevant prior experience and gaps in current knowledge.

Page 3 of 22 Revised: July 24, 2017

Gas permeable rigid contact lenses are commonly used as refractive treatment, for normal individuals, but also specifically for individuals with irregular ocular surfaces that require the rigid lens material to mask irregularities on the front refracting surface of their eye (the cornea). However, these lenses rely on surface treatments and coatings in order to improve their interactions with the front surface of the eye and the tear film, which are very sensitive tissues that can respond negatively to the rigid materials (for example: discomfort, dryness). Several studies have found that reducing the friction between the lens and the surface of the eye (as well as the eyelid) will improve the comfort of the lens while a patient is wearing them. The primary principle behind HydraPEG coating and Tangible Boost replenishing system is that they reduce friction between the lens and the eye surface and eyelids.

Contact lens manufacturers and distributors are continuously developing new products and technology to make the surface of a contact lens more compatible with the ocular surface. HydraPEG is a newly FDA approved coating that is available in the US and Europe, and the Tangible Boost treatment being evaluated here is an important component of maintaining this treatment of the lens surface.

2.2 Describe any relevant preliminary data. Reference previously approved IRB protocols (by number), if applicable.

Hydra-PEG (Ocular Dynamics, Menlo Park, CA) is a contact lens coating designed to improve the lens/ocular surface interface by mimicking the natural tear film's water content and wettability. A previous study done at UH showed that the coating improved comfort and vision when applied to scleral contact lenses. (ID# 16071-01). The Hydra-PEG coating is FDA approved for use as a contact lens coating.

2.3 Provide the scientific or scholarly background for, rationale for, and significance of the research based on the existing literature and how will it add to existing knowledge.

Knowledge gained by this work will increase our understanding of the surface characteristics of rigid lenses and the interaction of the lens surface with the ocular surface.

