3.0 Inclusion and Exclusion Criteria

3.1 Describe the specific criteria that define who will be included or excluded in your final study sample. Make sure to include age.

Page 4 of 22 Revised: July 24, 2017

The participant will be eligible to participate if the following criteria apply: 1. Written Informed Consent has been obtained prior to any study-related procedures taking place; 2. Written documentation has been obtained in accordance with the relevant county and local privacy requirements, where applicable (i.e., Written Authorization for Use and Release of Health and Research Study Information to obtain contact lens prescription and wearing information from their medical record should the subject be a patient at the UH College of Optometry); 3. Male or female,18 years of age and older prior to the initial visit; 4. Is an established scleral or corneal rigid contact lens wearer; 5. In the opinion of the investigator, the subject has the ability to follow study instructions; 6. In the opinion of the investigator, the subject has the ability to complete all study procedures and visits.

The participant would not be eligible to participate if at least one of the following criteria is met: 1. Has never worn either scleral or corneal contact lenses before; 2. Does not possess a usable pair of spectacles; 3. Has any ocular disease or abnormality that would affect the wearing of contact lenses; 4. Is aphakic (i.e., missing their natural lens inside the eye); 5. Is currently participating in any other type of eye-related clinical or research study; 6. Is pregnant or nursing as reported by the subject. 7. Has a condition or is in a situation which, in the investigator's opinion, may put the subject at significant risk, may confound study outcomes, or may significantly interfere with the subject's participation in the study. 8. Has a known and self-reported allergy to the following substances: Dextran, polyethylene glycol, hydroxypropyl methylcellulose, or polyvinyl alcohol, which are components of the Tangible Boost and HydraPEG systems. 9. Has had previous ocular surgery within the past 12 weeks.

3.2 Describe how potential subjects will be screened for eligibility based on these criteria.

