5.	Birthdate (mm/dd/yy):/				
6.	Gender: \square_1 Male \square_2 Female				
7.	Lens Indication:				
8.	Lens Type (circle one): Scleral	Corneal			
9.	Duration of lens wear (months/years):				
10.	Average # hours lens wear per week:				
11.	Hours of lens wear today:				
12.	CLDEQ-8 a. CLDEQ-8 completed and verified:	□₁ Yes	\square_2 No	CLDEQ-8 score:	
13.	VAS scale a. VAS scale completed and verified:	□ ₁ Yes	\square_2 No	VAS score:	
14.	Medications and Medical History a. Current medications or supplements?		□ ₁ Yes	\square_2 No	

UNIVERSITY of HOUSTON

15.

Diameter: ____ Lens Power:

Limbal Profile: _____

Landing Zone Profile: ______

Subject:	

_					
TH	IE OCULAR SURFACE INSTITUTE		Date:	/	/
	Evaluation of Tangible Boost F	Replenish	ing Syst	em	
c. d. e. f.	Was the concomitant medication log completed? Medical or ocular conditions? Was the medical and ocular history log completed? History of ocular surgeries, ocular injections or laser □₁ Yes □₂ No (If No, skip to question 10) Was the surgery more than 12 weeks ago? □₁ Yes Type of ocular surgery and when it occurred? /	\Box_1 Yes \Box_1 Yes procedures?	\square_2 No \square_2 No \square_3 N/A	ate:	/
Со	ntact lens history				
a.	Current lens brand				
00					
OS	·				
b.	Current lens parameters (if known)				
	Base curve:				
	SAG:				
	Diameter:				

c.	Did subject wear their own contact lenses 2 days prior to this appointment? \square_1 Yes \square_2	No

Visual Acuity with habitual lenses (logMAR): Record # of letters seen **16.**

OS: OD: _____

Over refraction (spherical only) **17.**

OD OS

Examiner Initials:

THE OCULAR SURFACE INSTITUTE

Sub	oject:		_
Date:	/	/	_

Evaluation of Tangible Boost Replenishing System

	OD			OS
		Movement		
		Centration		
		Apical Clearand	ce	
		Limbal Clearan	ce	
		Scleral Landing Z	one	
		Commonts		
Perform Kera	atograph NIBUT			
OD:	NIKf-BUT "until b	olink" (first break up)		
	NIKavg-BUT "unt	il blink" (average break up)		
	Level:			
	NIKf-BUT "25 sec	conds" (first break up)		
	NIKavg-BUT "25	seconds" (average break up))	
	Level:		7	
				
OS:	NIKf-BUT "until b	olink" (first break up)		
OS:	NIKf-BUT "until b NIKavg-BUT "unt	olink" (first break up) il blink" (average break up)		
OS:	NIKavg-BUT "unt	il blink" (average break up)		
OS:	NIKavg-BUT "unt Level:	il blink" (average break up) 		
OS:	NIKavg-BUT "unt Level:	il blink" (average break up) 		
OS:	NIKavg-BUT "unt Level: NIKf-BUT "25 sec	il blink" (average break up)		

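### The summary with and without HydraPEG compares habitual lenses of unrecorded coating with new coated AVT lenses, so the change cannot be attributed to the coating

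*Combined protocol and SAP*

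**What the plan says.** The Statistical Analysis paragraph of section 10.2 has three parts. It plans within-subject comparisons of before and after by paired non-parametric methods. It adds that "this baseline data will be compared to normative data available for a soft contact lens wearing population". It then plans descriptive statistics "to evaluate the overall response of the eye to a rigid lens with and without HydraPEG", and likewise with and without Tangible Boost. Section 25.1 adds that baseline and test data will be examined for differences by hypothesis tests.

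On the lenses, section 10.1 says "All subjects will be refit into the Advanced Vision Technologies (AVT) brand of rigid lenses", that the ordered study lenses carry the HydraPEG coating, and that current AVT wearers have their parameters re-ordered. Randomisation, at Visit 3, is between the Boost kit and the placebo kit only.

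On the subjects, inclusion criterion 4 in section 3.1 reads "Is an established scleral or corneal rigid contact lens wearer". Section 2.1 says "HydraPEG is a newly FDA approved coating that is available in the US and Europe", and section 2.2 cites a previous study of the coating on scleral lenses at the same university. Item 15 of the Visit 1 worksheet asks for "Current lens brand" and for the lens geometry and power.

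**The concern.** A summary labelled as with and without a coating invites the reader to take the difference as what the coating does. That needs two things: a state known to be uncoated, and nothing else of consequence changing between the two states. The plan secures neither.

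At stake is a secondary, largely descriptive reading of the data. A change after dispensing could be taken for a coating effect when it comes from a fresh or differently fitted lens. A real coating effect could also look smaller than it is because some habitual lenses were already coated. The soft-lens norms raise a separate question: it is unclear what a comparison with another lens type would tell the reader about this cohort.

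**Working it through.** The plan gives no figure for this contrast, so there is none to reproduce. The check sets the sections side by side and then shows how far the data could identify a coating effect.

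**1. What the uncoated state can be.** All dispensed study lenses are coated, and there is no period or arm with an uncoated AVT lens (section 10.1). A study lens worn for 30 days may have less coating (section 1.1 says it diminishes), but that is not a lens without it. Only the habitual lens before dispensing remains.

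**2. Whether that lens is known to be uncoated.**
- The coating is on sale (section 2.1).
- Most subjects are expected from the university's own specialty contact lens service (section 6.2).
- Neither the exclusion criteria (section 3.1) nor the screening questions in the appendix mention coated lenses.
- The legible Visit 1 worksheet has lens indication, type, wear history, brand and parameters. It has no field for coating, material or age of the current pair.

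**3. What else changes at dispensing.**
- Everyone gets a new lens.
- Fit and power may change, but not equally. AVT wearers are re-ordered (section 10.1). The Visit 1 worksheet orders corneal lenses from habitual parameters plus over-refraction and limits diagnostic fitting to scleral wearers. Section 10.1 says all undergo a diagnostic AVT fit, so the two need reconciling.
- A care product is specified with the study lenses, but section 10.1 names ClearCare and the handling sheet names Unique pH. These passages must also be reconciled. The habitual product is not asked about on the legible Visit 1 form; Visit 2 does record the current solution.

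**4. Identification.** Let c be the true coating effect, q the share of habitual lenses already coated, k the fraction of the full contrast that a worn coated lens still shows against a fresh one (0 to 1), and r the net effect of new lens, fit, care product and time. The expected change is

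D = c × [1 − q(1 − k)] + r

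The coating part shrinks by q(1 − k), which is at most q and equals q only when k = 0. The values of q, k and r below are assumptions. With c = 1 and k = 0:

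| q | D if r = 0 | D if r = 0.5 |
|---|---|---|
| 0 | 1.00 | 1.50 |
| 0.10 | 0.90 | 1.40 |
| 0.25 | 0.75 | 1.25 |
| 0.50 | 0.50 | 1.00 |

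A change of 1.00 fits q = 0 with r = 0, and equally q = 0.50 with r = 0.5. It also fits no coating effect at all (c = 0) with r = 1. With q = 0.50 and k = 0.5, the shrinkage is 0.50 × 0.5 = 0.25, half the bound.

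**5. If the change is tested.** Take the 30 analysed subjects (section 5.2), a two-sided 0.05 level (assumed; none is stated), a normal approximation to a paired test, c = 0, and r in standard deviations of the paired difference:

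P(significant) = Φ(r√30 − 1.96) + Φ(−r√30 − 1.96), with √30 = 5.477

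- r = 0: 0.05
- r = 0.3: Φ(1.643 − 1.96) gives 0.38
- r = 0.5: Φ(2.739 − 1.96) gives 0.78
- r = 0.8: Φ(4.382 − 1.96) gives 0.99

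Such a test would correctly detect a change. The error would lie in crediting it to the coating.

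**6. Soft-lens norms.** All subjects wear rigid lenses. Section 2.1 says such lenses are used in particular for irregular ocular surfaces, and the screening note allows the conditions they treat. A difference from soft-lens norms would mix lens type with population. Section 10.2 names no source, endpoint or purpose for the norms.

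**The case against.** The best defence is that this contrast is minor and loosely worded. The study goal is Boost (section 1.1). Section 10.2 calls the HydraPEG summary descriptive, and no section says that a change from the habitual lens will be reported as the effect of the coating. The questionnaire description in section 10.2 and the patient surveys already set habitual lenses against coated or Hydra-PEG lenses, which is close to the right label. Inclusion criterion 2 provides for authorisation to obtain prescription and wearing information for clinic patients, so coating status might be recoverable for some of them. All of this stands and limits the weight of the point. It does not supply a known uncoated state: the documents do not say that the records hold coating status, and the paired and hypothesis tests in sections 10.2 and 25.1 could be applied to the same change.

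Four stronger readings are tempting, and the documents do not support them.

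- *The main comparison is confounded.* It is not. Boost and placebo are randomised at Visit 3, after all subjects have moved to coated AVT lenses.
- *The soft-lens norms are meant to isolate the coating.* Section 10.2 applies them to baseline data and makes no such claim.
- *Fit, power and care product change for everyone.* AVT re-orders and corneal wearers are partial exceptions on fit and power, though they too get a new lens. A change of care product cannot be assumed for each subject.
- *The placebo arm can stand in for the uncoated state.* It wears coated lenses too, so it is a comparator for Boost only.

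**Conclusion.** The point holds as a limit on interpretation. As planned, the change from habitual to study lens cannot be attributed to HydraPEG, because the habitual coating is unrecorded and a new AVT lens arrives together with the coating. Dilution by already coated habitual lenses is possible but of unknown size. It is at most the share coated, and less if worn coating still differs from fresh. That bound assumes a worn coated lens shows between none and all of the full contrast. The direction and size of the new-lens effect are also unknown, so the net bias could go either way.

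The finding rests on the legible form text; a coating item lost in extraction would remove the dilution part but not the new-lens confounding. Importance is low: the contrast is secondary and the correction nearly free.

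**What to change.** - Add *habitual lens HydraPEG-coated: yes / no / unknown* to item 15 of the Visit 1 worksheet.
- In section 10.2, limit the summary without HydraPEG to subjects whose habitual lenses are confirmed uncoated, and show coated and unknown separately.
- Relabel the contrast *habitual lens versus new coated AVT lens*, and state that no effect is attributed to the coating alone. The new field deals only with dilution; the relabelling is what deals with the new lens and refit.
- Drop the soft-lens comparison, or keep it as descriptive context with a named source.
- State that the placebo arm is the comparator for Boost, not for HydraPEG.

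The cost is one form item and a few edited sentences. The downside is a smaller descriptive group, out of 30 analysed subjects, with small coated and unknown groups beside it.
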